10.1.6 Follow-up period

During the follow-up period, SAEs (regardless of relationship with study treatment) and IMP-related AEs ongoing at the end of study treatment, as well as new IMP-related AEs/SAEs, will be followed until resolution or stabilization, where stabilization is defined as an event ongoing without any change for at least 3 months. During the follow up period, patients will be followed up every 6 weeks (± 1 week) until death, study cut-off, or withdrawal of patient's consent, whichever comes first. For patients who discontinue study treatment prior to documented disease progression, a tumor assessment will be performed every 6 weeks. Date of disease progression and further anticancer treatment will be collected at the follow-up visit.

The following procedures will be performed/assessed:

- **ECOG PS and body weight.**
- **Tumor assessment** (if applicable, ie, if disease progression has not yet been documented).
- **Post-study treatments:** if used to treat new or unresolved treatment-related AEs.
- **Adverse events:** any treatment-related AEs and all SAEs ongoing at the end of study treatment, and new treatment-related AEs or SAEs will be recorded until recovery, or until the event has been stabilized.
- **Further anticancer therapy:** in case a patient discontinues study treatment due to a reason other than progressive disease, further antitumor therapy will not be initiated before progression is documented.

- [REDACTED]
- **Blood sampling for ATA:** as specified in PK/immunogenicity flow chart (see [Section 1.4](#)).

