2.1.3 Efficacy endpoints

2.1.3.1 Primary efficacy endpoint(s)

The primary efficacy endpoint will be the Overall Response Rate (ORR) defined as the proportion of patients with confirmed complete response (CR) or confirmed partial response (PR) as Best

Overall Response (BOR), assessed by the Investigator (based on RECIST 1.1), relative to the total number of patients in the efficacy population (see [Section 2.3.1](#)). Confirmation of objective responses will be performed by repeat tumor imaging (Computed Tomography [CT] scan, MRI) at least 4 weeks after the first radiological documentation of response.

Tumor assessments will be performed every 6 weeks (ie, every 2 cycles) during the treatment period and every 6 weeks during the follow-up period if a patient discontinues treatment prior to radiologic disease progression.

Tumor assessments after the initiation of post-treatment anti-cancer therapy will be excluded from the determination of Best Overall Response in a patient. See [Appendix B](#) (Determination of tumor response) for details.

Best Overall Response

BOR is the best tumor response observed from first study treatment infusion until disease progression, death or initiation of post-treatment anti-cancer therapy, whichever occurs first.

Primary ORR analysis can be performed when all patients treated in Part 2a and Part 2b have had at least 4 postbaseline tumor assessments, experienced confirmed objective response, or have discontinued the study for any reason. However, if the primary criteria of 7 responders is either met or not met with certainty at the end of the Part 2a in the selected dose when all patients have had 2 postbaseline tumor assessments, experienced confirmed objective response, or discontinued the study for any reason and when all the patients of the Part 2b have had 2 postbaseline tumor assessments, experienced confirmed objective response, or discontinued the study for any reason, analysis may be done at that time instead.

Best tumor shrinkage

For patients with measurable disease, the best tumor shrinkage will be defined by the best relative change from baseline as follows:

$$Y = 100 \times \frac{Y_{smallest} - Y_{baseline}}{Y_{baseline}}$$

Where Y is the sum of longest diameter of the target lesions.

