2.1.3.2.1 Duration of response

The duration of response will be defined as the time from the date of first initial occurrence of a subsequently confirmed CR or PR to the date of first radiological documentation of disease

progression (using RECIST 1.1) before the initiation of any post-treatment anti-cancer therapy or death (due to any cause), whichever occurs first.

Duration of response is determined only for patients who have achieved a response of confirmed CR or PR.

If a patient receives post-treatment anti-cancer therapy before radiologic progression or death, the duration of response will be censored at the date of the last valid response assessment without evidence of progression performed before the initiation of the post-treatment anti-cancer therapy.

If a patient receives post-treatment anti-cancer therapy without radiologic progression or death, the duration of response will be censored at the date of the post-treatment anti-cancer therapy.

In the absence of radiologic progression, death or post-treatment anti-cancer therapy, the duration of response will be censored at the date of the last valid response assessment without evidence of progression.

A valid response assessment is defined as a response assessment with a response different of NE.

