2.1.3.2.3 Time to progression

The time to progression is defined as the time interval from the date of first study treatment administration to the date of first radiologically documented tumor progression or death from disease progression before the initiation of any post-treatment anti-cancer therapy, whichever occurs first.

If a patient receives post-treatment anti-cancer therapy before radiologic progression or death, TTP will be censored at the date of the last valid response assessment without evidence of progression performed before the initiation of the post-treatment anti-cancer therapy.

If death different from disease progression occurs before receiving post-treatment anti-cancer, TTP will be censored at the date of the last evaluable response assessment without progression.

If a patient receives post-treatment anti-cancer therapy without radiologic progression or death, TTP will be censored at the date of the post-treatment anti-cancer therapy.

In the absence of tumor progression or death due to disease progression or post-treatment anti-cancer therapy, TTP will be censored at the date of the last valid response assessment without evidence of progression. An evaluable response assessment is defined as a response assessment with a response different of NE.

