 - If the day of the death date is missing, it will be imputed as the first day of the month, except if the date of the patient's last contact is in the same month as the death date. In this case, the death date is imputed as the date of last contact + 1 day.
 - If the day and month of the death date is missing, the date of death will be imputed to the first of January of the year, except if the date of the patient's last contact is in the same year as the death date. In this case, the death date will be imputed as the date of last contact + 1 day.
 - If the death date is missing, no imputation will be done and the patient will be censored at the last contact date.
- Incomplete date of first post-treatment anti-cancer therapy: if the day of first post-treatment anti-cancer therapy is missing, the date will be imputed to the first day of the month.

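### Imputing a missing therapy day to the 1st of the month can turn a documented progression into censoring for TTP and DOR, and can shorten SD duration

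*SAP*

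**What the plan says.** SAP 2.5.3 sets the rule for an incomplete date: "if the day of first post-treatment anti-cancer therapy is missing, the date will be imputed to the first day of the month". No exception is given. The death-date rule in the same list also defaults to the 1st, "except if the date of the patient's last contact is in the same month as the death date", in which case death is placed one day after last contact.

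The therapy date then decides what counts:

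- **TTP (SAP 2.1.3.2.3).** The event is radiological progression "or death from disease progression before the initiation of any post-treatment anti-cancer therapy, whichever occurs first". If therapy comes first, "TTP will be censored at the date of the last valid response assessment without evidence of progression performed before the initiation" of that therapy.
- **DOR (SAP 2.1.3.2.1).** Progression counts "before the initiation of any post-treatment anti-cancer therapy or death (due to any cause), whichever occurs first", with the same censoring rule.
- **Stable-disease duration for DCR (SAP 2.1.3.2.2).** If therapy comes first, the duration ends at the last valid non-progression scan before it.
- **BOR (SAP 2.1.3.1 and Appendix B).** "Tumor assessments after the initiation of post-treatment anti-cancer therapy will be excluded from the determination of Best Overall Response in a patient".
- **Primary PFS (SAP Appendix F, Table 20).** New anti-cancer therapy is ignored.

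On the expected order of events, Protocol 6.2.1 has patients treated until radiological progression, unless toxicity or refusal intervenes. For those who stop for a reason other than progression, Protocol 10.1.6 states that "further antitumor therapy will not be initiated before progression is documented".

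**The concern.** The protocol's own sequence is progression, then new therapy. Moving an incomplete therapy date back to the 1st reverses that sequence whenever both fall in one month and the progression is dated the 2nd or later. It can even place the new therapy before the last SAR566658 infusion.

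For TTP and DOR, a known event is then replaced by censoring at the preceding scan. The patients censored are exactly those who have just progressed, so the non-informative censoring that Kaplan-Meier estimation relies on fails, and both endpoints are biased upward. For DCR the direction is opposite: a shortened stable-disease duration can fall below 3 months and remove a patient from disease control.

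**Working it through.** The plan gives no figure for this rule, so the check follows it through the endpoint definitions and then sizes it under stated assumptions.

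**1. One patient, DCR and TTP.** Scans are every 6 weeks (SAP 2.1.3.1). Take SD at week 12, PD at week 18, and new therapy later in the month of that PD with the day not recorded.

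- True order: SD duration = 18 × 7 = 126 days; TTP is an event at 126 days.
- Imputed order: PD falls after the 1st, so SD duration = 12 × 7 = 84 days and TTP is censored at 84 days.
- The shortest run of three calendar months is 28 + 31 + 30 = 89 days. At 84 days the patient no longer has disease control.

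**2. Share affected, given a missing day.** Let therapy start g days after PD, with PD dates spread evenly over the calendar. In a month of L days, the affected PD dates run from the 2nd to day L − g, which is L − g − 1 days. The mean month over 1,461 days (48 months) is 30.44 days, so the share is about (30.44 − g − 1)/30.44. An exact calendar count gives:

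| Assumed gap g | Share affected |
|---|---|
| 7 days | 74% |
| 14 days | 51% |
| 21 days | 28% |
| 28 days | 5% |

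A PD dated the 1st ties with the imputed date. The SAP states no tie rule; I count that PD as kept.

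**3. Lost TTP events.** The documents give neither the missing-day rate nor the proportion going on to further therapy. Assume 20 of the 29 patients do, with 5% to 20% of days missing:

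- 28-day gap, 5% missing: 20 × 0.05 × 0.05 = 0.05
- 14-day gap, 10% missing: 20 × 0.10 × 0.51 = 1.0
- 7-day gap, 20% missing: 20 × 0.20 × 0.74 = 3.0

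DOR includes confirmed responders only. With 7 responders and the same proportion treated further, 7 × 20/29 = 4.8 patients are exposed. That gives at most 4.8 × 0.20 × 0.74 = 0.7 lost events.

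**4. Size of the TTP bias.** Assume exponential TTP with a 12-week median and 6-weekly scans. The chance of PD per interval is h = 1 − 2^(−0.5) = 0.293. If a fraction f of PD events is instead censored at the previous scan, each interval's Kaplan-Meier factor rises from (1 − h) to (1 − h)/(1 − fh). The 12-week estimate is the square of that factor:

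- f = 0: 0.707² = 0.500
- f = 5%: (0.707/0.985)² = 0.515
- f = 10% (about 3 of 29 events): (0.707/0.971)² = 0.531

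**The case against.** A reader might infer that the rule threatens the primary endpoint, because BOR drops scans after new therapy and one lost responder at the boundary is decisive: under a 12% null, 7/29 gives p = 0.052 and 6/29 gives p = 0.127, against a one-sided 10% level. The documents do not support giving this weight. The usual scan lost from BOR is a progression scan. At most BOR then moves from PD to NE, and SAP 2.5.3 counts a non-evaluable patient as a non-responder anyway. Losing a response requires the confirming CR/PR scan and the start of new therapy in the same month. With therapy held until progression is documented (Protocol 10.1.6) and scans every 6 weeks, that should be rare.

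A reader might also see any disagreement between TTP and PFS as evidence of the fault. Largely it is not: TTP stops at new therapy and PFS ignores it, so the two can differ even with complete dates. PFS does supply an analysis that keeps the progression.

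Other points stand in part:

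- Further therapy is collected at 6-weekly follow-up visits, and eCRF data are queried (Protocol 13.4), so missing days may be close to none.
- TTP and DOR are descriptive; no test or decision rule uses them.
- The death-date safeguard prevents an impossibility, death before a known contact, whereas therapy before a scan can happen. The comparison shows that a guard is easy to write, not that its absence here is an oversight.
- Appendix B keeps a disease assessment whose scans straddle the therapy date. That clause concerns BOR only and does not rescue an ordinary single scan.

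None of this answers the TTP, DOR and stable-disease problem when a day is missing.

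**Conclusion.** The concern holds for TTP, DOR and the stable-disease duration behind DCR. For a missing day, the rule as written reverses the protocol's expected order for any progression dated the 2nd or later in the therapy month, and the resulting censoring is informative. The direction is clear: TTP and DOR upward, DCR downward.

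The frequency is not known. The 74%, 51%, 28% and 5% shares depend on assumed gaps and apply only to patients with a missing day. The 0.05 to 3 lost TTP events also depend on assumed rates of missing days and further therapy, and the count is zero if every day is recorded. Even at the top of that range, the illustrative 12-week TTP estimate moves only from 0.50 to 0.53. Primary PFS is unaffected, and the ORR conclusion is not at material risk. It is a modest flaw in secondary endpoints, worth correcting because the correction is cheap.

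**What to change.** In SAP 2.5.3, for TTP, DOR and stable-disease duration only: when the day of first post-treatment therapy is missing, impute the latest of (a) the 1st of the month, (b) the day after the last SAR566658 infusion, and (c) the day after a progression documented in that month. Cap the result at month end, and state that a progression on the imputed date counts as before therapy. Add month-end imputation as a sensitivity analysis.

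Leave the BOR rule unchanged. Extending the floor to every same-month scan could credit SAR566658 with a response seen on later therapy, which is the wrong direction of error for an open-label, investigator-assessed ORR.

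The cost is a sentence or two in the SAP and a small programming change before database lock, with no effect on sample size, power or alpha. There are two downsides. A progression truly seen after new therapy began in the same month would be counted as an event. And a patient could be NE for BOR yet have a TTP event, because the two would use different imputed dates.

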2.5.4 Missing data

In general, no imputation is planned for missing data. The following approaches are default methods for missing data handling.

For categorical variables, patients with missing data are not included in calculations of percentages unless otherwise specified. When relevant, the number of patients with missing data is presented.

Continuous data: the analyses and summaries for variables with continuous scales will be based on observed data only. However, the number of patients with missing observations will be provided.

Incomplete date of initial cancer diagnosis

If the day of initial cancer diagnosis is missing, the date will be imputed to the first day of the month.

Incomplete start/end date of prior anti-cancer therapy

If the day of start date of prior anti-cancer therapy is missing, the date will be imputed to the first day of the month.

If the day of end date of prior anti-cancer therapy is missing, the date will be imputed to the last day of the month.

Handling of medication missing/partial dates

No imputation of medications start/end dates will be performed (other than prior and further anti-cancer therapy). If a medication date is missing, so it cannot be determined whether it was taken prior or concomitantly, it will be considered as a prior, concomitant, and a post-treatment medication.

Handling of adverse events with missing or partial date/time of onset

Missing or partial adverse event onset dates and times will be imputed so that if the partial adverse event onset date/time information or visit number does not indicate that the adverse event started prior to treatment or after the treatment-emergent adverse event period, the adverse event will be classified as treatment-emergent. No imputation of adverse event end dates/times will be performed. These data imputations are for categorization purpose only and will not be used in listings. No imputation is planned for date/time of adverse event resolution

Handling of missing assessment of relationship of adverse events to investigational medicinal product

If the assessment of the relationship to IMP is missing, then the relationship to IMP has to be assumed and the adverse event considered as such in the frequency tables of possibly related adverse events, but no imputation should be done at the data level.

Handling of missing grades of adverse events

If the grade is missing for one of the treatment emergent occurrences of an AE, the maximal severity on the remaining occurrences will be considered. If the severity is missing for all the occurrences, no imputation will be done and the AE will be reported in all grades.

Handling of potentially clinically significant abnormalities

If a patient has a missing baseline he will be grouped in the category “normal/missing at baseline.”

For PCSAs with 2 conditions, one based on a change from baseline value or a normal range and the other on a threshold value, with the first condition being missing, the PCSA will be based only on the second condition.

2.5.5 Windows for time points

Summaries by cycles focusing on exposure and tumor assessments will be tabulated based on cycles as recorded in the e-CRF. For specific measurements such as vital signs and laboratory parameters, window defined around the date of treatment may be considered.

2.5.6 Unscheduled visits

Unscheduled visit measurements of laboratory data, vital signs, and ECG will be used for computation of baseline and worst values and/or grades.

2.5.7 Pooling of centers for statistical analyses

Data from all sites will be pooled together for analyses.

2.5.8 Statistical technical issues

Not applicable

3 INTERIM ANALYSIS

Interim analyses of efficacy, safety, and other data will be performed after 14 patients are treated at each dose level at the end of Part 1. These interim analyses are planned to occur when all patients have completed at least 4 postbaseline tumor assessments, experienced confirmed objective response, or discontinued the study for any reason. However, if the futility criteria of 2 responders is either met or not met with certainty for both arms when all patients have completed 2 postbaseline tumor assessments, experienced confirmed objective response, or discontinued the study for any reason, the analyses may be conducted at that time instead. Enrollment will be interrupted after completion of enrollment in Part 1, until completion of the Part 1 interim analysis.

An interim analysis based on efficacy will be performed to assess futility (to reject early the hypothesis that the response rate is 30%). If there is 0 or 1 response (CR or PR) in the first 14 patients treated at each dose, the 7.1% critical boundary is not met and the alternative hypothesis of at least 30% will be rejected. If the critical boundary of 7.1% is reached (2 responses or more), the study can continue in Part 2 at the selected dose.

At the same interim analysis, overwhelming efficacy will be assessed (to reject early that the response rate is less than or equal to 12%). If there are 6 responses or more in the first 14 patients treated at 1 dose, the critical boundary of 42.9% (1-sided nominal significance level of 2%) is reached and the null hypothesis of 12% will be rejected.

Overall, this procedure has 80% statistical power (1-sided alpha level of 10%) to reject the null hypothesis, using a gamma (-2) beta spending function for futility analysis and a Lan DeMets (OF) alpha spending function in a 1 sample test for a binomial proportion (East version 6.3 using exact computations, Cytel Software, Cambridge, MA)

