	
alpha level of 10%. An interim analysis is planned in Part 1 after 14 patients have been treated at each dose.
 
Part 1
 
An interim analysis will be performed to assess futility (to reject early the hypothesis that the response rate is 30%). If there is 0 or 1 response (CR or PR) in the first 14 patients treated at each dose, the critical boundary 7.1% is not met and the alternative hypothesis of at least 30% will be rejected. If the critical boundary of 7.1% is reached (2 responses or more), the study will continue in Part 2 at the selected dose.
 
At the same interim analysis, overwhelming efficacy will be assessed (to reject early that the response rate is less or equal to 12%). If there are 6 responses or more in the first 14 patients treated at 1 dose, the critical boundary of 42.9% is reached and the null hypothesis of 12% will be rejected.
 
Overall, this procedure has 80% statistical power (1-sided alpha level of 10%) to reject the null hypothesis, using a gamma (-2) beta spending function for futility analysis and a Lan-DeMets (OF) alpha spending function in a 1 sample test for a binomial proportion (East version 6.3 using exact computations, Cytel Software, Cambridge, MA).
 
The dose selection will be done at the end of Part 1, following decision criteria explained in the study design section.
 
Part 2a
 
A total of 7 confirmed responses (CR or PR) or more out of 29 patients (patients from Part 1 and Part 2a at the selected dose) will be necessary to reject the null hypothesis at the end of the Part 2a expansion/overexpressing CA6 cohort.
 
• Sample size determination for the Part 2b (mild CA6 expression cohort) 
At the selected dose, the relationship between CA6 expression level and efficacy outcomes will be assessed by adding a cohort of 20 patients with mild CA6 membrane staining (with at least 1% positive tumor cells at intensity $\geq 1+$ and $< 30\%$ of tumor cells at intensity of 2+, 3+).
 
With a sample size of 20 patients, a true response rate above 15% can be rejected with 83% confidence if we observe 0 or 1 response.
 
Moreover, if we observe 7 responses in the 29 patients in the CA6 overexpression cohort ($\geq 30\%$, 2+/3+) and ≤ 1 response in the mild CA6 expression cohort (CA6 IHC = ($< 30\%$ 2+, 3+ and at least 1% positive cells at intensity $\geq 1+$), the 1-sided p-value (according to Fisher's exact test) will be around 7% suggesting an association between biomarker status and ORR.
 
Analysis population:
 
Safety population: The all treated population consisting of patients who will actually receive at least 1 dose (or any partial) of SAR566658. This population is the primary population for the analyses of efficacy and safety parameters.

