11.5 INTERIM ANALYSIS

Interim analyses of efficacy, safety, and other data will be performed after 14 patients are treated at each dose level at the end of Part 1. These interim analyses are planned to occur when all patients have completed at least 4 postbaseline tumor assessments, experienced confirmed objective response, or discontinued the study for any reason. However, if the futility criteria of 2 responders is either met or not met with certainty for both arms when all patients have completed 2 postbaseline tumor assessments, experienced confirmed objective response, or discontinued the study for any reason, the analyses may be conducted at that time instead. Enrollment will be interrupted after completion of enrollment in Part 1, until completion of the Part 1 interim analysis.

An interim analysis based on efficacy will be performed to assess futility (to reject early the hypothesis that the response rate is 30%). If there is 0 or 1 response (CR or PR) in the first 14 patients treated at each dose, the 7.1% critical boundary is not met and the alternative hypothesis of at least 30% will be rejected. If the critical boundary of 7.1% is reached (2 responses or more), the study can continue in Part 2 at the selected dose.

At the same interim analysis, overwhelming efficacy will be assessed (to reject early that the response rate is less than or equal to 12%). If there are 6 responses or more in the first 14 patients treated at 1 dose, the critical boundary of 42.9% (1-sided nominal significance level of 1.8%) is reached and the null hypothesis of 12% will be rejected.

Overall, this procedure has 80% statistical power (1-sided alpha level of 10%) to reject the null hypothesis, using a gamma (-2) beta spending function for futility analysis and a Lan-DeMets (OF) alpha spending function in a 1 sample test for a binomial proportion (East version 6.3 using exact computations, Cytel Software, Cambridge, MA).

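### The interim and final response counts are right, but the 7.1% futility boundary, the 1.8% or 2% level given for 6/14, and the 7% Fisher p-value are wrong or mislabelled

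*SAP*

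**What the plan says.** The interim look comes after 14 patients at each dose. For zero or one response, SAP section 3 (like protocol 11.5) says "the 7.1% critical boundary is not met and the alternative hypothesis of at least 30% will be rejected". It then says "If the critical boundary of 7.1% is reached (2 responses or more), the study can continue in Part 2 at the selected dose". Protocol 11.5 and the Statistical considerations part of the protocol synopsis describe 7.1% in the same way; the synopsis reads "If the critical boundary of 7.1% is reached (2 responses or more), the study will continue in Part 2 at the selected dose".

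The early-rejection rule applies "If there are 6 responses or more in the first 14 patients treated at 1 dose". The two documents attach different levels to it:

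- SAP section 3: "the critical boundary of 42.9% (1-sided nominal significance level of 2%) is reached and the null hypothesis of 12% will be rejected"
- Protocol 11.5: "the critical boundary of 42.9% (1-sided nominal significance level of 1.8%) is reached and the null hypothesis of 12% will be rejected"

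SAP 1.6 declares no statistical changes made in the SAP.

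For Part 2b, the protocol synopsis takes 7 responses in 29 overexpressing patients and at most 1 in 20 mild-expression patients, and states that "the 1-sided p-value (according to Fisher's exact test) will be around 7% suggesting an association between biomarker status and ORR". Protocol 11.1.2 and SAP 1.3.2 give the same figure.

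**The concern.** Three printed figures do not match the counts beside them.

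1. One response in 14 is 7.1%. A result the plan calls futile therefore already reaches the boundary that it is said to miss. The 42.9% boundary works the other way: it equals 6/14, a rate at which its rule does trigger.
2. One boundary carries two levels, 1.8% and 2%, and both texts cite exact computations. An exact level for 6/14 at 12% should be far smaller than either.
3. The Fisher p-value looks slightly low for the counts given.

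These figures describe the go/no-go and early-rejection rules for the primary endpoint and the rationale for the Part 2b cohort. A report that cited the percentage or the level instead of the count would misstate the rule.

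**Working it through.** **Inputs.** Null rate 12%, alternative 30%, one-sided alpha 10%, power 80%, final rule 7 or more of 29 (SAP 1.3.2; protocol 11.1.1). Interim rules at 14 patients: 0-1 futile, 6 or more rejects the null (SAP 3; protocol 11.5). Spending functions: gamma(-2) for beta, Lan-DeMets (OF) for alpha. Part 2b: 7/29 against 1/20.

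**The plan's counts reproduce.** With X1 responses in the first 14 patients and X2 in the next 15, the chance of rejecting the null is P(X1 ≥ 6) + Σ(x = 2 to 5) P(X1 = x)·P(X2 ≥ 7 − x).

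- At 30% this is 0.8004, matching the stated 80% power.
- At 12% it is 0.0501, within the 10% ceiling. A final cut-off of 6/29 would give 0.117, so 7 is the smallest valid count at 29 patients.
- Futility: the gamma(-2) beta spend at t = 14/29 is 0.20 × (1 − e^(2t))/(1 − e^2) = 0.0509. P(X ≤ 1 | 14, 0.30) = 0.0475 fits within it; P(X ≤ 2) = 0.1608 does not.
- Efficacy: the Lan-DeMets (OF) spend at t = 14/29 is 2 × [1 − Φ(z(0.95)/√t)] = 0.0179. P(X ≥ 6 | 14, 0.12) = 0.0038 fits; P(X ≥ 5) = 0.0196 does not. Six is therefore the right count.

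**Figure 1, futility percentage.** 1/14 = 7.14% and 2/14 = 14.29%. So 7.1% is the highest futile rate, and the lowest rate that allows continuation is 14.3%. One response is a common result: at 12%, P(X = 1 | 14) = 0.319 per arm. The better of two such arms has exactly one with probability P(X ≤ 1)² − P(X = 0)² = 0.4859² − 0.1670² = 0.208.

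**Figure 2, level of 6/14.** The exact level is P(X ≥ 6 | 14, 0.12) = 0.00379, or 0.38% per arm. The chance that at least one of two arms at 12% reaches it is 1 − (1 − 0.00379)² = 0.0076. The protocol's 1.8% is the allotted cumulative alpha (1.79%). Normal-approximation tests of 6/14 give 0.02% (null variance) and 0.98% (observed variance), so they explain neither printed value. The SAP's 2% could be 1.8% rounded. It also equals the spend at t = 0.5 (2.00%), which would fit the superseded 28-patient design in SAP Table 1; the documents do not say which. The rounding is unhelpful because the exact level of 5/14, 1.96%, lies between 1.8% and 2%: a 2% limit would admit five responses, and a 1.8% limit would not.

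**Figure 3, Fisher test.** Given 8 responders among 49 patients, the hypergeometric probabilities are:

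- 7 of the 8 in the group of 29: C(29,7)·C(20,1)/C(49,8) = 0.0692
- all 8 in the group of 29: C(29,8)/C(49,8) = 0.0095

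The one-sided p-value is 0.0692 + 0.0095 = 0.0787. The observed table alone gives 6.9%, and 7/28 against 1/20 gives 7.1%; either could be the source of the printed figure. With no responses in the mild cohort, the p-value for 7/29 against 0/20 is 0.0182.

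**The case against.** The strongest reply is that this is editorial. Every passage that prints 7.1% also prints the count, and other sections state the rule in counts alone, so a reader would have to ignore the same sentence to go wrong. The 1.8% is correctly computed by the named spending function and is only mislabelled, and 2% may be no more than rounding. The Fisher figure is an approximate planning illustration with no threshold attached; SAP 2.4.6.2 will compute the test from the observed data.

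Most of this stands, and it is why the point is minor. The 1.8% can stay under the right label, and where the 2% came from cannot be settled. The chance of seeing exactly 1/14 is not the chance of a wrong decision, which the counts prevent. But neither document says that the counts govern, 7.1% is not a rate that only two or more responses reach, rounding does not turn 0.38% into 1.8% or 2%, and 7.87% rounds to 8%.

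**Conclusion.** The concern holds and is minor. Three printed figures need correcting; the design does not. The exact level of 6/14 is 0.38% per arm against 1.8% or 2% printed, the continuation threshold is 14.3% against 7.1% printed, and the Fisher p-value is 7.9% against about 7% printed. No count, sample size or decision changes.

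The 0.38% level and the 5.0% type I error are single-arm figures, and protocol 11.4.4.4 and SAP 2.4.4.3 make no adjustment for dose selection. If both arms have a 12% response rate, the arm with more responses is always carried forward, and either arm reaching 6/14 rejects the null, the type I error is about 8.8%, still below 10%. That selection rule is an assumption, since the actual choice also weighs safety.

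**What to change.** In protocol 11.5 and SAP 3, state that the counts govern and use the same figures in both:

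- futile at 0-1/14 (7.1% or less); may continue from 2/14 (14.3% or more);
- reject the null at 6/14 or more (42.9% or more), with allotted cumulative alpha 1.8% and attained exact one-sided level 0.38% per arm, before dose selection.

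Correct the futility percentage in the protocol synopsis too. Keep the existing text on acceptable safety and on not selecting a dose with fewer than two responses; this change does not replace it.

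In the protocol synopsis, protocol 11.1.2 and SAP 1.3.2, give the Fisher p-value as about 8% with one response in the mild cohort and about 2% with none. The 83% confidence figure just before it can be corrected at the same time: 1 − P(X ≤ 1 | 20, 0.15) = 82.4%.

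The cost is wording only, in the synopsis, protocol 11.1.2 and 11.5, and SAP 1.3.2 and 3.
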